5.3.3 Activity

Strenuous activity is prohibited from 48 hours prior to admission to the Clinical Research Unit (CRU) until discharge from the CRU.

5.4 Screen failures

Screen failures are defined as subjects who signed the ICF to participate in the clinical study but are not subsequently randomized. A minimal set of screen failure information is required to ensure transparent reporting of screen failure subjects to meet the Consolidated Standards of Reporting Trials (CONSORT) publishing requirements and to respond to queries from regulatory authorities. Minimal information includes demography, screen failure details, eligibility criteria, and any serious adverse event (SAE).

Individuals who do not meet the criteria for participation in this study (screen failure) may not be rescreened.

These subjects should have the reason for study withdrawal recorded in the electronic Case Report Form (eCRF).

6 STUDY TREATMENTS

Study treatment is defined as any IP (including marketed product comparator and placebo) or medical device(s) intended to be administered to a study participant according to the CSP.

Study treatment is to be administered in the morning under fasted conditions. Subjects will fast overnight (nothing to eat or drink except water) for at least 10 hours before receiving study treatment. Subjects will remain fasted for 4 hours after dosing with study treatment.

6.1 Treatments administered

6.1.1 Investigational products

Table 8 Study treatments

Study treatment name:	AZD4041
Dosage formulation:	[REDACTED]
Strength/Concentrations:	[REDACTED]
Placebo:	[REDACTED]
Route of administration:	Oral
Dosing instructions:	Oral syringe
Packaging and labelling:	Formulation to be prepared extemporaneously from drug substance at the clinical site. Stock solutions to be prepared on a weekly basis and stored under refrigerated conditions (2°C to 8°C). Dosing solutions to be prepared on a daily basis for use within 24 hours and may be stored under ambient conditions.
Provider:	AMRI, Albany, New York

6.2 Preparation/handling/storage/accountability

The Investigator or designee must confirm appropriate temperature conditions have been maintained during transit for all study treatment received and any discrepancies are reported and resolved before use of the study treatment.

Only subjects enrolled in the study may receive study treatment and only authorized site staff may supply or administer study treatment. All study treatments must be stored in a secure, environmentally controlled and monitored (manual or automated) area, in accordance with the labelled storage conditions, with access limited to the Investigator and authorized site staff.

Details of study treatment preparation and administration are given in the Handling Instructions.

A formal system for drug accountability will be implemented. The Investigator, institution, or the head of the medical institution (where applicable) is responsible for study treatment accountability, reconciliation, and record maintenance (ie, receipt, reconciliation, and final disposition records).

6.3 Measures to minimize bias: randomization and blinding

PPD will generate the randomization schedule. Eligible sentinel subjects within each cohort will be randomly assigned in a ratio of 1:1 to Active:Placebo after all entry criteria have been satisfied before dosing on Day 1. Following review of sentinel safety data up to 24 hours post-dose, the remaining subjects within each cohort will be randomly assigned in a ratio of 5:1 to Active:Placebo.

6.3.1 Blinding Procedures

This is a double-blind study. Neither the subjects nor the investigator will be aware of the treatment assignment. Blinding will be maintained throughout the study by use of active and placebo dosage forms of similar appearance. Access to the randomization code will be strictly controlled according to the standard operating procedures of PPD.

6.3.2 Breaking the Blind

Blind breaking envelopes will be prepared. A subject or subjects may be unblinded in the event of a dose-limiting toxicity, SAE, or other event, or if there is a medical emergency where the identity of the drug must be known to properly treat a subject. A cohort may be unblinded to determine if dose escalation to the next dose level will terminate. If a subject becomes seriously ill or pregnant during the study, the blind will be broken only if knowledge of the administered study drug will affect that subject's treatment options. In the event of a medical emergency requiring identification of the study drug administered to an individual subject, the investigator will make every attempt to contact the medical monitor to explain the need for opening the code within 24 hours of opening the code. The investigator will be responsible for documenting the time, date, reason for the code break, and the names of the personnel involved.

6.4 Treatment compliance

Any change from the dosing schedule, dose interruptions, dose reductions, or dose discontinuations should be recorded in the eCRF.

The Investigator is responsible for management of the IP from receipt by the study site until the destruction or return of all unused IP.

6.5 Concomitant therapy

Any medication or vaccine including over-the-counter or prescription medicines, vitamins, and/or herbal supplements that the subject is receiving at the time of enrollment or receives during the study must be recorded along with:

- Reason for use

- Dates of administration, including start and end dates
- Dosage information, including dose and frequency

Table 9 Restricted medications

Medication/class of drug:	Usage (including limits for duration permitted and special situations in which it is allowed):
Antacids Analgesics other than paracetamol/acetaminophen Herbal remedies Megadose (20 to 600 times recommended daily dose) vitamins Megadose minerals	In the 2 weeks prior to administration of IP, or longer if the medication has a long half-life, use of any of these medications constitutes a basis for exclusion from the study.
Grapefruit juice	Subjects should not consume grapefruit juice for up to 7 days before dosing and throughout the study.

IP Investigational product

Table 10 Prohibited medications

Prohibited medication/class of drug:
Any other investigational drugs than provided in this study
Any medication with enzyme inducing properties such as St John's wort
Hormone replacement therapy
Oral and topical inhibitors/inducers of CYP3A4
Vaccination with COVID-19 vaccine less than 14 days prior to the proposed date of randomization

Medication other than that described above, which is considered necessary for the subject's safety and wellbeing, may be given at the discretion of the Investigator and recorded in the appropriate section of the eCRF.

7 DISCONTINUATION OF TREATMENT AND SUBJECT WITHDRAWAL

7.1 Discontinuation of study treatment

As individual subjects are given only one dose of IP, there are no criteria for discontinuing study treatment. This section describes the criteria for study termination and the discontinuation of planned dose escalations within the study.

The sponsor designee reserves the right to close the study site or terminate the study at any time for any reason at the sole discretion of the sponsor.

The study may be stopped if, in the judgement of AstraZeneca, trial subjects are placed at undue risk because of clinically significant findings that:

- Meet individual stopping criteria or are otherwise considered significant
- Are assessed as causally related to IP
- Are not considered to be consistent with continuation of the study

Regardless of the reason for termination, all data available for the subject at the time of discontinuation of follow-up must be recorded in the CRF.

In terminating the study, the sponsor will ensure that adequate consideration is given to the protection of the subjects' wellbeing.

After each cohort, an SRC will review and assess all the available safety and PK data from all of the cohorts to date in order to make a decision on the dose for the next cohort of subjects.

Data from a minimum of 6 subjects dosed per cohort must be reviewed before each dose escalation.

If any of the following scenarios occur within a cohort with a reasonable possibility of a causal relationship with AZD4041, escalation to the next, higher dosage level may not occur:

General

- One or more subjects, who receive AZD4041, report a SAE or experience AEs judged to be non-tolerable by the PI or the SRC, and are deemed related to AZD4041.

Cardiovascular criteria

- Two or more subjects, who receive AZD4041, have QTc prolongation defined as QTcF >500 ms, or a prolongation from baseline of >60 ms, confirmed (persistent for at least 5 minutes) and determined post-dose either during continuous 12-lead ECG monitoring or on a repeat 12-lead ECG.
- Two or more subjects, who receive AZD4041, have tachycardia defined as resting supine HR >125 beats per minute persisting for at least 10 minutes.
- Two or more subjects, who receive AZD4041, have symptomatic bradycardia defined as resting supine HR <40 beats per minute or asymptomatic bradycardia defined as resting supine HR <30 beats per minute while awake and persisting for at least 10 minutes.
- Two or more subjects, who receive AZD4041, develop hypertension defined as an increase in resting supine systolic BP >40 mmHg to above 180 mmHg and persisting for at least 10 minutes.
- Two or more subjects, who receive AZD4041, develop hypotension defined as an asymptomatic fall in systolic BP of >20 mmHg to <70 mmHg persisting for at least

10 minutes, or a symptomatic fall in resting supine BP >20 mmHg (excluding vasovagal reaction).

- Two or more subjects, who receive AZD4041, have tachycardia defined as resting supine heart rate >125 beats per minute persisting for at least 10 minutes.
- Two or more subjects, who receive AZD4041, have a non-sustained ≥ 5 beat if “slow” (<100 bpm), or “fast” (≥ 100 bpm) ventricular tachycardia.
- One or more subjects, who receive AZD4041, have a sustained ventricular tachycardia (ie, >30 second duration, or leading to hemodynamic consequences requiring immediate arrhythmia termination).

Laboratory findings

- One or more subjects, who receive AZD4041, fulfill Hy’s Law defined as “An increase in aspartate aminotransferase (AST) or alanine aminotransferase (ALT) ≥ 3 x upper limit of normal (ULN) and total bilirubin (TBL) ≥ 2 x ULN, where no other reason can be found to explain the combination of increases; eg, elevated serum alkaline phosphatase (ALP) indicating cholestasis, viral hepatitis, or another drug.” The elevations do not have to be at the same time or within a specified time frame.
- Two or more subjects, who receive AZD4041, have >3 x ULN of either ALT or AST, or >2 x ULN for TBL or ALP.

Criteria for halting dose escalation

PK data indicate that the predefined maximum exposure level/maximum plasma concentration (free C_{max} of [REDACTED])

[REDACTED] has been achieved, or is predicted to be achieved or exceeded should the dose be increased as planned. The exposure limits should be applied on mean values within a cohort. If this halting dose escalation criterion is met, the SRC will stop any further dose escalation. The SRC will determine whether a lower or the same dose should be tested or whether the study should be terminated.

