Study drug administration				X				
Adverse event recording	X	X	X	X	X	X	X	X
Blood pressure, temperature, respiratory rate, and pulse rate	X		X	X ^d	X	X	X	X
12-lead paper safety ECG	X		X	X ^e	X ^e	X ^e	X ^e	
12-lead digital ECG				X ^e	X ^e	X ^e	X ^e	
Telemetry ^f			X	X				
Clinical laboratory evaluations ^g	X		X		X			X
Physical examination	X		X				X	X
Blood sampling for PK ^h				X	X	X	X	
Blood sampling for testosterone, LH, FSH, and inhibin B (male subjects only) ⁱ			X	X	X	X	X	

^a Tests will be performed at follow-up and also in cases of discontinuation.

^b Serum pregnancy test will be performed at screening and check-in.

^c Height will be measured at screening only.

- d Blood pressure, temperature, respiratory rate, and pulse rate will be measured at pre-dose, then at 1, 2, 3, 4, 6, 8, 12, 24, and 48 hours post-dose.
- e Paper and digital ECGs will be collected at the same time points as PK sampling. Recording of ECGs will precede PK sampling and check of vital signs at each time point.
- f For all subjects in Cohort 4 and first 5 subjects in Cohort 5: Telemetry for 4 to 6 hours on Day -1 to establish a baseline. Pre-dose to 24 hours post-dose. For the remaining subjects in Cohort 5 and all subjects in Cohort 6: Telemetry for 24 hours on Day -1, and pre-dose to 48 hours post-dose.
- g Clinical laboratory assessments must be repeated if first collected more than 2 weeks before dosing.
- h Blood samples will be collected at pre-dose, then at 0.25, 0.5, 1, 1.5, 2, 3, 4, 6, 8, 12, 24, 36, 48, and 72 hours.
- i Male subjects only: samples for testosterone, LH, FSH, and inhibin B will be collected at 0 hour (0800 or 1000) and at 4, 6, 8, 12, 22, and 24 hours on Day -1 and at 0 hour (0800 or 1000) and at 1, 2, 4, 6, 8, 12, 24, 36, 48, and 72 hours on Day 1 to Day 3. The '0' hour time point should be approximately the same time that dosing is scheduled for on Day 1. On Day 1, samples for testosterone, LH, FSH, and inhibin B will be collected at the same time as PK samples.

BMI body mass index; CRU Clinical Research Unit; ECG electrocardiogram; FSH follicle stimulating hormone; HIV human immunodeficiency virus; LH luteinizing hormone; PK pharmacokinetic(s)

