Given that the exposure limits are predicted to be reached at [REDACTED], only vasectomised male and female subjects of non-childbearing potential will be enrolled in the remaining cohorts (Cohort 4 onwards). The highest dose that could be explored in these remaining cohorts will be determined by the exposure cap based on the NOAEL exposure in female dogs, from the 28-day repeat dose toxicity study.

The safety data from the sentinel subjects up to 24 hours post-dose will be reviewed by the Principal Investigator (PI), Clinical Research Organization (CRO) Medical Monitor, and AstraZeneca Study Physician before the remaining subjects in the cohort are dosed. The remaining 6 subjects for each cohort will be dosed at least 24 hours after the sentinel cohort.

Safety review committee

A Safety Review Committee (SRC) will review data from each cohort before progression to the next cohort occurs.

Statistical methods

Safety, tolerability, and pharmacokinetic (PK) data will be summarized descriptively as appropriate. Descriptive summary statistics for continuous variables will include number, arithmetic mean, standard deviation, minimum, median, and maximum, while for continuous PK variables, descriptive summary statistics will also include geometric mean and arithmetic coefficient of variation. Descriptive summary statistics for categorical data will include frequency and proportion. Tests of significance of group difference (drug dose versus placebo) on change from baseline in safety variables will also be performed. Model-based approaches will be used, if appropriate.

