In the hERG assay, the [REDACTED]. In a panel of in vitro electrophysiological assays of recombinant human voltage-gated cardiac ion channels (hKv4.3/hKChIP2.2 – ITO; hKv7.1/hKCNE1 – IKS; hNav1.5 – INa; hKV1.5; hCav3.2; hHCN4) - AZD4041 had no activity. Therefore, a risk of QT prolongation is not expected with AZD4041. In the dog cardiovascular study, sustained durations of premature ventricular contractions, beginning approximately 7 hours after dosing and continuing up to 24 hours after dosing, [REDACTED]. The onset of the changes was soon after the approximate T_{max} [REDACTED] in the dog study. Hemodynamic parameters were largely unaltered and were maintained in the physiological range of heart rate and blood pressure. In a dog 14-day investigative study, lower heart rate, with associated higher PR and QT intervals were recorded at [REDACTED]; there were no changes in the rate-corrected QT interval and no arrhythmias were noted. There were no changes in ECG rhythm or waveform morphology attributable to AZD4041. Furthermore, there were no effects on ECG parameters or morphology in a 28-day dog study in which dogs received up to [REDACTED].

[REDACTED]

Table 3

CV Cardiovascular; PO Oral

While it is unclear what physiological mechanisms could be responsible for the observed arrhythmias, further risk mitigation measures are being added to the protocol in the form of extending the pre-dose telemetry for 24 hours on Day -1 to identify and exclude subjects at higher risk of arrhythmia events, extending the continuous cardiac telemetry for the first 48 hours after dosing, in addition to the regular monitoring for heart rate (HR) and blood pressure (BP). Subjects older than 55 years will be excluded in order to reduce the risk of observing benign background arrhythmic events, which are typically seen in older individuals. Stopping criteria based on corrected electrocardiogram (ECG) Q-T interval (QTc), HR and BP have been included in this FIH study.

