For the purpose of a single dose study, testicular toxicity is not considered to be relevant for vasectomised male or female subjects of non-childbearing potential. Therefore, given that the exposure limits are predicted to be reached at doses [REDACTED] only vasectomised male and female subjects of non-childbearing potential will be enrolled in the remaining cohorts. The highest dose that could be explored in these remaining cohorts will be determined by the exposure cap based on the NOAEL exposure in female dogs, from the 28-day repeat dose toxicity study [REDACTED]
[REDACTED].

In addition to the above risk mitigation strategies, a number of other measures are being taken in this study to minimize any potential risk to participants, given that this is an FIH administration of this compound. The key measures among these include the following:

- This study will employ sentinel dosing, whereby only 2 subjects (1 active + 1 placebo) will be dosed in a blinded manner at the start of a cohort and their safety will be monitored for 24 hours before dosing the rest of the cohort;
- Further, this study will enroll only healthy non-smokers who will be carefully selected based on exhaustive inclusion and exclusion criteria to avoid placing such subjects at any significant risk;
- In addition, subjects will be confined to an in-patient unit that specializes in and is equipped for the conduct of FIH studies, starting from the day prior to dosing and for 72 hours after dosing.

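### Cohort 6: telemetry was lengthened to 48 h against NSVT, but the rest of the cohort may still be dosed 24 h after the sentinel pair

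*Protocol*

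**What the plan says.** **Telemetry.** Protocol 2.2.2 reports premature ventricular contractions in the dog cardiovascular study, from about 7 h until as late as 24 h after dosing, and says the mechanism is unclear. It adds mitigation measures, among them "extending the continuous cardiac telemetry for the first 48 hours after dosing". Section 2.2.3 calls the package adequate for a potential NSVT risk. The package is longer telemetry before and after dosing, exclusion on abnormal pre-dose telemetry, and a lower age limit.

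Table 2 footnote f says who gets the longer recording. "For all subjects in Cohort 4 and first 5 subjects in Cohort 5: Telemetry for 4 to 6 hours on Day -1", then to 24 h after dosing. The longer schedule is for the remaining Cohort 5 subjects "and all subjects in Cohort 6: Telemetry for 24 hours on Day -1, and pre-dose to 48 hours post-dose". According to section 2.3, five of the eight Cohort 5 subjects had already been dosed.

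**Sentinel release.** Section 1.2 has three physician-level roles review the sentinel data up to 24 h, and adds: "The remaining 6 subjects for each cohort will be dosed at least 24 hours after the sentinel cohort". Section 2.2.2 lists it as a key safeguard that "their safety will be monitored for 24 hours before dosing the rest of the cohort". Section 6.3 says that after the 24 h review "the remaining subjects within each cohort will be randomly assigned in a ratio of 5:1 to Active:Placebo". None of these makes an exception for Cohort 6, and SAP 3.1 and 4.1 repeat the 24 h.

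**Escalation.** The NSVT criterion in section 7.1 counts AZD4041 subjects who "have a non-sustained ≥ 5 beat if “slow” (<100 bpm), or “fast” (≥ 100 bpm) ventricular tachycardia". It needs two or more, states no time window, and governs the step from one cohort to the next.

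The SAP schedule (14.1) still shows 24 h of telemetry after dosing for Cohorts 4 to 6. This point takes protocol Table 2 as governing.

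**The concern.** The added hours were meant to address NSVT, yet in Cohort 6 the sentinel step does not wait for them. Each subject receives a single dose, so a finding in the sentinel at 30 h or 40 h cannot undo the dosing of the other six. It can only change how they are watched.

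Cohort 6 is the last planned cohort, so no planned escalation decision follows it. Release of the remaining six is the one planned dosing decision left at that dose. Safety is the primary objective and telemetry is a named primary endpoint. What is at stake is whether five AZD4041 subjects are dosed before anyone at that dose has completed the monitoring period that the sponsor itself thought worth adding.

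**Working it through.** **1. The plan's own counts.** 6 cohorts × 8 subjects = 48, as stated. Per cohort: AZD4041 1 sentinel + 5 = 6; placebo 1 sentinel + 1 = 2, as stated.

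**2. Cohort 6 timeline at the earliest permitted release**

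| Hours from sentinel dose | Sentinel pair (1 AZD4041, 1 placebo) | Other six (5 AZD4041, 1 placebo) |
|---|---|---|
| 0 to 24 | first half of telemetry | not dosed |
| 24 | 24/48 = half complete; reviewed data end here | may be dosed |
| 24 to 48 | second half of telemetry | their own first 24 h |
| 48 | telemetry complete | already 24 h after dosing |

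Subjects at the Cohort 6 dose with telemetry through hours 24 to 48 at release: none under a 24 h hold; two, one of them on AZD4041, under a 48 h hold.

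**3. What the previous dose contributes.** Cohorts 1 to 4 and the first five of Cohort 5 have telemetry to 24 h after dosing (footnote f of Tables 1 and 2). In Cohort 5, 8 − 5 = 3 subjects have 48 h. The first five are the sentinel pair and three of the block of six, which holds one placebo. If the order within that block is random, the placebo is among the last three with probability 3/6 = 1/2. So 2 or 3 AZD4041 subjects have telemetry past 24 h, each with probability 1/2.

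The other five Cohort 5 subjects still have 12-lead ECGs at 36, 48 and 72 h. Table 12 schedules 5-minute digital extracts. Those ending at 36 h and 48 h cover 2 × 5 = 10 minutes of the 24 × 60 = 1440 minutes between 24 h and 48 h, or 0.7%. They show intervals and sustained rhythm changes but can miss short runs.

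**4. Is there exposure after 24 h?** Section 2.3 says three Cohort 3 subjects had more than 20% of AUC0-inf extrapolated; sampling ended at 48 h. Assuming the last quantifiable sample was at 48 h:

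- Without a model, the share after 24 h exceeds the share after 48 h, so it is above 20%.
- One compartment with fast absorption: exp(−48k) > 0.20, so k < ln(5)/48 = 0.0335 per h, half-life > 20.7 h, and share after 24 h > √0.20 = 0.447.
- With an early distribution phase and an assumed terminal half-life of 40 h: share after 24 h > 0.20 × 2^(24/40) = 0.303.

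This shows that exposure continues in some subjects. It does not show that arrhythmia starts after 24 h.

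**5. Gain from a 48 h hold.** Let p be the probability that an AZD4041 subject has a first ventricular run in hours 24 to 48. The chance of seeing such a run before the rest are dosed is 0 under a 24 h hold and 1 × p = p under a 48 h hold. The documents give no basis for p.

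**The case against.** The best case for the present text has four parts.

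- The only described signal began at about 7 h, soon after Tmax, and continued up to 24 h. A 24 h hold covers its onset, and concentrations are past peak afterwards. This stands and is the main reason to rate the point low. The documents do not say whether the dog recording went beyond 24 h.
- Sections 2.2.2 and 2.2.3 present the 48 h telemetry as monitoring, not as a condition for dosing. This also stands: the plan does not contradict itself.
- The 24 h interval is a minimum, so the reviewing physicians may wait longer. True, but nothing asks them to, and the data specified for their review end at 24 h.
- Telemetry is displayed live (8.2.5.3), the other six are themselves monitored in the unit, and one AZD4041 sentinel adds little detection. All true. Live display protects each monitored subject, but it cannot withdraw a dose already given.

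What remains against the objection is the low cost: the recording is already planned, and only the release time would change.

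**Conclusion.** The point holds as a cheap improvement, to be considered. At the last planned dose, five AZD4041 subjects may be dosed before any subject at that dose has been on continuous telemetry through hours 24 to 48. At the previous dose only 2 or 3 AZD4041 subjects will have had it. The benefit of waiting equals one subject's unknown late-run probability. The conclusion assumes that Cohort 6 is given a new dose (the Safety Review Committee, SRC, may repeat or lower it), that release happens at the earliest permitted time, and that Table 2 footnote f is followed.

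A reader might infer something stronger: that the step from Cohort 5 to Cohort 6 can also be taken without the late hours. Section 7.1 says "Data from a minimum of 6 subjects dosed per cohort must be reviewed before each dose escalation", and 6 − 5 = 1, so at that minimum only one subject has telemetry past 24 h and late runs alone could not reach the two-subject NSVT threshold. The arithmetic is right, but the documents do not support the conclusion. The SRC assesses all available safety and PK data, with safety follow-up to Day 15 as available and PK sampling to 72 h. Every Cohort 5 subject has ECGs at 36, 48 and 72 h. The NSVT criterion has no time limit, eight subjects are planned, and escalation needs the principal investigator's agreement. Section 4.3 places the detailed data requirements in the SRC Charter, which is not among these documents. The first five Cohort 5 subjects were dosed before telemetry was lengthened, and that cannot be repaired now. Nor do the documents show that the 24 h hold is unsafe.

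**What to change.** In protocol 1.2, 2.2.2 and 6.3, add for Cohort 6:

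*In Cohort 6, the remaining 6 subjects will be dosed at least 48 hours after the sentinel subjects, after review of safety data including telemetry up to 48 hours post-dose.*

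SAP 3.1 and 4.1 repeat the 24 h text and should follow. The NSVT criterion in 7.1 needs no change for this purpose.

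The cost is one extra day between the sentinel pair and the rest, in one cohort. No procedure is added: the sentinel subjects already stay in the unit to Day 4 and are on telemetry to 48 h.
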